#### **Primary care**

We will use the Clinical Practice Research Datalink (CPRD) to access electronic health records (EHRs) from primary care practices. The database holds anonymised general practice records on all registered patients, including diagnoses, test, prescribed treatments and referrals. Each interaction with a health professional is recorded, through unique identifiers for patients, consultations and health professionals. The staff role field can be used reliably to identify the type of GP (partner, salaried, or locum) involved in any recorded interaction. In addition, linkage to Hospital Episodes Statistics (HES) data is available. This allows us to obtain detailed information on any form of hospital attendance for all patients in the practices that are part of this linkage scheme. Our proposal plans to use data from both CPRD Gold (practices using Vision software) and the more recent CPRD Aurum (practices using EMIS). In total we should be able to access data from about 1,100 practices for a median period of 10 years, involving millions of patient, the great majority of which have given permission for the practice data to be linked to HES.

We will analyse the data in bins of financial years. Within each financial year, our population will comprise of patients registered with a CPRD general practice for whole of the year. Preliminary analyses in CPRD have confirmed that the available staff role identifier is widely and reliably used across practices, and we will use it to identify locum and permanent GPs. This will be our key parameter of interest and we will evaluate its association with important patient outcomes. All analyses will be conducted at the patient level.

We will focus on service utilisation and patient outcomes. Our primary outcomes will be patients revisiting the general practice within 7 days or 15 days. Secondary outcomes will include: referrals to secondary care, unplanned hospital admissions within 7 days or 15 days (through HES linkage), A&E attendance within 7 days or 15 days (through HES linkage), ambulatory care sensitive conditions (ACSC) hospitalisations within 7 days or 15 days (through HES linkage), antibiotic prescriptions, and validated prescribing safety indicators (as established measures of clinical performance and quality of care) which we have already used in a prior study using the CPRD.(44)

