All analyses will be controlled for available patient, general practitioner and general practice characteristics. Patient: age, sex, deprivation as measured by the 2015 Index of Multiple Deprivation (IMD, in quintiles),(45) years registered with the practice (if not collinear with age), number of practice visits in the previous financial year (or in the previous 12 months since the current consultation event) and numerous chronic conditions which are well recorded in these databases since they are part of the Quality and Outcomes Framework (atrial fibrillation, asthma, cancer, coronary heart disease, chronic kidney disease, chronic obstructive pulmonary disease, dementia, depression, diabetes, epilepsy, heart failure, hypertension, limiting disabilities, severe mental health, osteoporosis, peripheral arterial disease, rheumatoid arthritis and stroke).(46) General practitioner: sex/age are unavailable, but see analytical plan below). General practice: list-size, urban/rural location, practice location IMD (in quintiles), region, ratio of locum consultations over total within the

respective analysis year. We will also derive and describe consultation characteristics, like type, length and day of the week, although these will be used for descriptive purposes.

Our power calculation is based on the primary outcome, revisiting general practice within 7 days, and on the assumption that 10% of patients consulting a permanent GP return within that time period. Assuming 9 consultations with a permanent GP for 1 consultation with a locum, an alpha level of 5%, and an increase in the outcome to 15% for locum consultations (OR=1.59), we would need a total of 4330 patients to have 90% power to detect the association. Although this approach ignores between-practice variability in both the intercept and the association (e.g. varying return rates for permanent GPs and locus), it does demonstrate that we have many hundreds (if not thousands) times the numbers needed to detect a meaningful association.

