All outcomes and key covariates of interest will be appropriately described over time, at the patient, GP and general practice level. For example, we will plot the percentage of revisits within 7 days by locum/permanent GP groups, across all practices, over time. We will use multi-level mixed effects logistic regression models to quantify the association between the exposure of interest (locum/permanent GP) and the outcomes of interest, controlling for all available covariates previously discussed. If an outcome (e.g. safety indicators) in better expressed as a count, e.g. if we identify that numerous indicators tend to apply to visits, we will use multi-level mixed effects Poisson or negative binomial regression models instead. Analyses will be conducted at the patient level, accounting for the nested structure of the data: patients within general practices, within regions. We will include random effects for practices and possibly for regions (alternatively a fixed effect for regions).

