First, we will focus on prescribing activity which can be linked to a single locum. Specifically, by comparing prescribing practices using both established prescribing safety indicators developed for primary care but adapted for this setting(50) and EPR data on rates and outcomes of clinical pharmacist reviews/interventions (i.e. if the prescription is changed). Multivariate regression analysis will be used and safety indicators /pharmacist review outcomes will be the dependent variable. The independent variable will be binary, indicating whether the activity was performed by a locum. We will control for patient and ward characteristics which may be prescribing outcomes and treatment by locum (for example age, gender, speciality).

Our second approach will consider each entire patient admission and approximate the proportion of care delivered by locum doctors. For example if during their admission a patient has two interactions (such as tests or prescriptions) recorded by a locum doctor but six ordered by a permanent doctor, the proportion would be 0.25. This measure will be used as the independent variable when examining length of stay, rates of emergency readmission and mortality. With this analysis occurring in one trust only we will carefully consider if we have the power to detect meaningful associations. If under-powered, the processes developed could be applied to more trust EPR data in the future. Indeed, having undertaken this work successfully with Salford Royal NHS Foundation Trust, we will if time and resources allow seek to extend it to other hospitals in the Northern Care Alliance Group with similar EPR capabilities.

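### The WP4 primary-care model has no GP level although locum status belongs to the GP, so the standard error of the locum effect is too small if GPs within a practice differ

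*Protocol*

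**What the plan says.** All of this is in Protocol section 5, WP4, Primary care.

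- **Exposure.** It comes from the GP's recorded role: "The staff role field can be used reliably to identify the type of GP (partner, salaried, or locum) involved in any recorded interaction".
- **GP identifier.** One is available: "Each interaction with a health professional is recorded, through unique identifiers for patients, consultations and health professionals".
- **Model.** A multi-level mixed-effects logistic regression, with Poisson or negative binomial for counts, "accounting for the nested structure of the data: patients within general practices, within regions". The random terms are stated: "We will include random effects for practices and possibly for regions", with a fixed region effect as the alternative.
- **GP level.** It is named for the descriptive summaries only. GP age and sex are not available as covariates.
- **Sampling.** One consultation is drawn at random per patient within each financial year. The unmatched regression is primary, and the same models are used on the matched samples.
- **Power.** 10% against 15%, 9:1, alpha 5%, 90% power and 4330 patients in total. The text concedes that this "ignores between-practice variability in both the intercept and the association". It says nothing about variation between GPs.

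**The concern.** Within a practice, exposure is constant for a given GP record, so the GP is a cluster that carries the exposure. Drawing one consultation per patient per year prevents a patient from counting twice within a year. It does not prevent many patients of the same GP from entering the analysis. A practice random effect absorbs only what all GPs of the practice share. Differences between GPs in how often patients return, or in prescribing, stay unmodelled, and the missing GP age and sex leave nothing to explain them. The model then treats patients of one GP as independent given the practice.

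At stake are the confidence interval and p-value of the primary locum estimate. An understated standard error makes chance differences between a few locums and a few permanent GPs look like an effect of locum status.

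**Working it through.** **1. The protocol's own figure.** The Wald formula for a log odds ratio, two-sided 5% (sidedness is not stated), 90% power, 9:1:

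N = 10 × (1.960 + 1.282)² × [1/(0.15×0.85) + 1/(9×0.10×0.90)] / (ln OR)²

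The bracket is 9.078. ln OR is 0.4626 (OR 1.588). N = 4457, or 4432 if OR is set to 1.59. Both are within 3% of the stated 4330, at which power by this formula is 89.2%. The figure reproduces approximately, and the calculation contains no clustering term.

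**2. Inputs for the check.** From the protocol: the 9:1 ratio and the 10% revisit rate. Assumed, because the protocol gives no values: per practice, 6 permanent GPs with 300 sampled consultations each (1800) and 3 locums with 66 each (198), which keeps about 9:1; and a between-GP SD, s, of 0.1 to 0.3 on the logit scale.

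**3. Formula.** For a within-practice comparison with equal-sized GPs in each group:

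- Variance that the practice-only model reports: v = 1/(198×0.09) + 1/(1800×0.09) = 0.0561 + 0.0062 = 0.0623.
- Variance that it omits: e = s² × (1/3 + 1/6) = 0.5 s².
- True SE over model SE: r = √(1 + e/v).
- Actual type I error: 2 × [1 − Φ(1.96/r)].

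| GP SD | e | r | Type I error |
|---|---|---|---|
| 0.1 | 0.005 | 1.04 | 5.9% |
| 0.2 | 0.020 | 1.15 | 8.8% |
| 0.3 | 0.045 | 1.31 | 13.5% |

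The number of practices cancels out of r, so a larger database does not remove the inflation.

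**4. Dependence on consultations per locum.**

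- 20 locums × 10 consultations (still 9:1): v = 0.0617 and e = s² × (1/20 + 1/6). This gives r = 1.07 at SD 0.2 and 1.15 at SD 0.3.
- 3 locums × 200 consultations (600 against 1800, or 3:1, not the protocol's ratio): v = 0.0247. This gives r = 1.35 at SD 0.2 and 1.68 at SD 0.3.

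**5. Simulation.** Data with between-GP variance were analysed with practice intercepts only (100 practices, 5 permanent GPs × 180, 2 locums × 50, 300 runs). Coverage of the nominal 95% interval was 95.0%, 95.7%, 92.3%, 88.7% and 77.0% for GP SD 0, 0.1, 0.2, 0.3 and 0.5. With 20 locums × 5 patients the SE ratio was 0.99, 0.99 and 1.04 at SD 0.1, 0.2 and 0.3. The practice-only model is calibrated when GPs do not differ and fails progressively as they do.

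**6. What this means at full size.** Scaling v to the roughly 1,100 practices in the protocol, the model SE is √(0.0623/1100) = 0.0075. Around OR 1.59 the interval is 1.57 to 1.61, and with r = 1.31 it is 1.56 to 1.62. For significance, the model needs an OR above exp(1.96×0.0075) = 1.015. With r = 1.31 the correct threshold is about 1.020.

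**The case against.** The strongest reply is that the size is unknown and may be trivial. The protocol gives no between-GP variance, and locum work may be spread over many doctors who each contribute few sampled patients. Steps 4 and 5 show that the inflation can then almost vanish. At the planned effect, the interval around 1.59 barely moves. Both points stand, and they limit the claim. They do not remove it, because the protocol lists its levels explicitly and leaves out the one that carries the exposure. The planned E-values, and the sensitivity analysis that drops experienced permanent GPs, address confounding rather than the standard error.

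A reader might go further in several ways that the document does not support:

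- **That the interval is bound to be too narrow, or that millions of records make the GP component dominate.** The ratio depends on consultations per GP, not on the total. At 9:1 with 3 locums × 66, the omitted part is 0.020/0.082 = 24% of the true variance at SD 0.2 and 0.045/0.107 = 42% at SD 0.3.
- **That a practice-level random slope for locum is wrongly missing.** The remark on varying association describes what the power calculation leaves out. The wording on random effects for practices does not exclude a slope, and this is ordinary SAP detail.
- **That a patient term is missing across years.** The analysis is described by financial year, and pooling of years is not stated.
- **That the hospital prescribing analysis has the same defect.** The protocol says "The independent variable will be binary, indicating whether the activity was performed by a locum" but fixes no error structure there, and it calls the work a limited feasibility study. Silence is not an error.

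**Conclusion.** The point holds in conditional form. The primary-care model as written omits the GP level, so the standard error of the locum effect is too small whenever GPs of the same practice differ materially. Under the assumed 9:1 layout, the true standard error is about 1.04 to 1.31 times the model's for a GP SD of 0.1 to 0.3, with type I error of about 6% to 13.5%. It is larger with more consultations per locum and negligible with few. These sizes rest on assumed GP numbers, consultations per GP and between-GP variance, none of which the protocol supplies.

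Power for OR 1.59 is not in question. The exposure is to small effects: under these assumptions, odds ratios within about 2% of 1 could be declared significant when they should not be. This should be corrected before analysis, but it does not invalidate the design.

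**What to change.** In the WP4 CPRD models, matched and unmatched, add a random intercept for the GP, identified by the staff identifier within practice, so that the stated nesting becomes patients within GPs within practices within regions. If that model cannot be fitted at this size, keep the practice model and report GP-cluster-robust standard errors. The identifier is already in the data, so nothing new has to be collected. The cost is a change of wording, more computing time and somewhat wider confidence intervals. If between-GP variance proves negligible, the results will hardly change.

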Our recent international review of the literature on locum working (17) identified eight key factors through which locum working may affect the quality and safety of patient care and which may also provide the basis for mechanisms or interventions designed to improve the quality and safety of locum working. These factors are summarised in table 1, and we plan to use this framework to structure and guide our fieldwork and analysis.

Theme	Theme description
Governance and patient safety	Locums are on the fringes of governance. Gaps in the oversight of locums continue to be a
	patient safety risk e.g. background checks. The short-term nature of locum work means that
	locums are less likely to take part in clinical governance activities, such as audits and
	continuing professional development (CPD).
Policies, procedures and continuity of	Locums are less likely to be aware of contextual issues and local policies and procedures that
care	are relevant to providing safe and effective care, especially if they do not receive adequate
	induction and briefing when they take up a locum role in a new/unfamiliar organisation.
	Locums are not prepared for practise in the same way as permanent staff – for example,
	inductions are often poor or absent meaning locums are unable to carry out their duties
	safely and efficiently. Other risks include not knowing how to escalate concerns, and being
	placed in challenging environments where staffing is an issue. Procedures may be less likely
	to be carried out when a locum is on duty. The use of locums presents a patient safety issue
	and may have a negative impact on continuity of care.
Impact on the healthcare team –	Locums (particularly short-term locums) can place burden on other members of the
scope of practice	healthcare team, such as nurses and junior doctors, who could be expected to perform
	outside of their scope of practice to compensate for a locum's lack of contextual/local
	knowledge/competencies.
Impact on the healthcare team –	Locum working can increase workload for other members of the healthcare team, for
workload	example, extra support for the locum who is unlikely to be familiar with policies and
	protocols and patients returning to see their regular GP.
Information exchange – patients	The quality and quantity of patient information may be reduced when locums are employed
	as locums are less likely to be familiar with the patient group and how to report and

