Data will be complete (e.g. a patient either is coded as having diabetes or not) and of high quality since tied to financial incentives (e.g. QOF) or almost impossible not to record (e.g. consultation, or prescribing). Therefore, we will not need to use a multiple imputation framework or anything similar. Confounding is a concern, with urgent requests perhaps being more likely handled by locums – e.g. a patient cannot afford to wait for 2 weeks before his/her regular GP is back from holiday. We will partly attempt to control for that through the available patient characteristics, but we will also interpret our results with caution and use the recently suggested E-Value to assess the potential effect of unmeasured confounding.(47) The age of GPs is not available in the database, and another concern is that locums may be much less experienced that permanent GPs, hence any potential differences could be attributed to that rather than the locum status. Although we need to be careful not to "overcontrol" the analyses for the characteristics of locum GPs, since numerous GPs close to or in retirement choose to locum, we will conduct a sensitivity analysis where we will exclude more experienced permanent GPs (thus focusing on GP registrars, salaried GPs and GP retainers vs locums, repeating all analyses previously described).

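### The completeness claim for the WP4 primary care data is not shown to cover GP-recorded referrals, so a lower locum referral rate could partly reflect recording, and no planned analysis would reveal it

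*Protocol*

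**What the plan says.** All the main statements are in Protocol section 5, WP4, Primary care.

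- **Completeness.** The data are described without exception: "Data will be complete (e.g. a patient either is coded as having diabetes or not) and of high quality". The reason given is that items are of this quality "since tied to financial incentives (e.g. QOF) or almost impossible not to record (e.g. consultation, or prescribing". The conclusion drawn is: "Therefore, we will not need to use a multiple imputation framework or anything similar".
- **Outcome and source.** The list reads "Secondary outcomes will include: referrals to secondary care, unplanned hospital admissions within 7 days or 15 days (through HES linkage". A&E attendance and ACSC hospitalisation carry the same linkage tag; referrals do not. The database description puts referrals in the practice record: "The database holds anonymised general practice records on all registered patients, including diagnoses, test, prescribed treatments and referrals".
- **Linkage.** HES is said to supply "detailed information on any form of hospital attendance for all patients in the practices that are part of this linkage scheme".
- **Framework.** In section 4, the Table 1 row on information exchange about patients says that "locums are less likely to be familiar with the patient group and how to report and", and continues with handing over patient information to other health professionals. The row describes reduced information as something that may happen. The protocol says this framework will shape both fieldwork and analysis.

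**The concern.** A referral with no entry in the practice record is scored as no referral. That does no harm to the locum comparison if omissions are equally common after locum and permanent consultations. It matters if they are not, because the error then depends on the exposure.

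The protocol names a route by which information from locum consultations could be poorer. It then declares the data complete, on grounds that fit diagnoses, consultations and prescriptions but are not argued for referrals. A recording difference could therefore be reported under RQ3 as a difference in clinical practice. A large sample does not help: it makes the estimate more precise without moving it closer to the truth.

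**Working it through.** The protocol gives no referral rate or recording rate, so there is no stated figure to reproduce. Its only sample size concerns revisits within 7 days and has no bearing here.

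**Step 1: do the stated reasons reach each outcome?** (WP4, Primary care)

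| Outcome | Apparent source | Covered by a stated reason? |
|---|---|---|
| Revisit within 7 or 15 days (primary) | Practice consultations | Yes, consultation is named |
| Antibiotics, prescribing safety indicators | Practice prescribing | Yes, prescribing is named |
| Unplanned admission, A&E, ACSC | HES linkage | Does not rest on GP coding |
| Referral to secondary care | Practice record (inferred) | Not shown |

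Referral is the one outcome for which neither a stated reason nor hospital linkage is given.

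**Step 2: would a planned analysis detect differential recording?** The E-value addresses unmeasured confounding. Covariate adjustment and propensity matching balance patients. The sensitivity analysis that drops more experienced permanent GPs addresses experience. Practice random effects do not remove a locum/permanent difference within a practice. None examines whether the outcome is recorded equally in the two groups.

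**Step 3: illustration of direction and size.** Assumptions, none of them from the protocol: true referral is 8% in both groups (true OR = 1) and permanent-GP capture is 95%.

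Recorded rate = true rate × capture. OR = [p_L/(1 − p_L)] / [p_P/(1 − p_P)].

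Permanent: 0.08 × 0.95 = 0.076; odds 0.076/0.924 = 0.0823.

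| Locum capture | Recorded locum rate | Odds | Spurious OR |
|---|---|---|---|
| 95% (equal) | 0.076 | 0.0823 | 1.00 |
| 90% | 0.072 | 0.0776 | 0.94 |
| 85% | 0.068 | 0.0730 | 0.89 |
| 80% | 0.064 | 0.0684 | 0.83 |

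**Step 4: wider range.** With true referral from 5% to 20%, permanent capture from 90% to 100%, and locum capture at 0.98 to 0.80 of permanent capture, the spurious OR runs from about 0.98 to 0.76. It is below 1 throughout because every case in the range assumes poorer locum capture.

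**Step 5: would it look significant?** Take one million patients at the protocol's planning ratio of nine permanent consultations to one locum, ignoring clustering, with 7.2% v 7.6%. SE = √(0.072 × 0.928/100,000 + 0.076 × 0.924/900,000) = 0.000864, and z = 0.004/0.000864 ≈ 4.6. The protocol expects millions of patients. At a 10% true rate with complete permanent capture, a relative shortfall of 5% reaches 90% power at a total of about 412,000, and one of 2% at about 2.6 million.

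**The case against.** The strongest reply is that the bias is conjectural. Table 1 says information may be reduced, and it concerns reporting and handover between professionals; it does not mention referral codes. A reader might infer that locums are expected to under-record referrals and that the result will therefore read as lower locum referral. The protocol does not support that. It raises a possibility, and extending it to referral entries is a further step. This part of the objection stands.

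A reader might also infer that only referrals entered by the index doctor count. Nothing says so: outcomes are aligned to the event date and analysed at patient level, so entries by any staff member could already be included. The exact definition and window may properly sit in the SAP, which was not available.

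Three further points have force. The examples behind the completeness claim are illustrative, so referrals are not expressly declared complete. Dismissing imputation is reasonable for codes that are simply present or absent; the issue is misclassification, which imputation would not ordinarily address. Referral is one of several secondary outcomes, and being listed first gives it no priority; the primary outcome is unaffected. The protocol also promises cautious interpretation.

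The breadth of the completeness statement remains. It makes no exception, its reasons are not shown to reach referrals, and nothing planned would reveal unequal recording.

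**Conclusion.** The concern holds as a limited one. The protocol claims completeness more widely than its reasons support, and for referrals that leaves a possible recording difference by GP type untested. If locum recording were poorer, the estimate would shift towards locums referring less.

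The size is unknown. The ORs of 0.94 to 0.83 rest wholly on the assumed 8% true rate, 95% permanent capture and 90% to 80% locum capture; with equal capture the OR is 1. That referral comes from the practice record is itself inferred, from the missing linkage tag and the database description. The point affects the interpretation of one secondary outcome and calls for an inexpensive improvement; it does not show that the referral analysis is biased.

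**What to change.** 1. In WP4, Primary care, confine the completeness statement to the items its reasons cover, and say that referrals may be under-recorded.
2. Keep GP-recorded referral as the outcome and state its source.
3. In HES-linked practices, add a sensitivity analysis of first outpatient attendance after the index consultation, using the same model. Report, separately for locum and permanent index consultations, the share of those attendances with a preceding referral code.
4. Interpret a referral difference as a difference in practice only if this check agrees.

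**Cost.** One extra outcome and one descriptive table, using outpatient records within the planned linkage, which is described as covering hospital attendance of every kind. Attendance is a noisier proxy: it depends on waiting times and on whether patients attend, it includes referrals by other clinicians, and it exists only for linked practices. It is therefore a check on the recorded outcome and should not replace it.
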